11.3.7.1 Systolic Ejection Time

SET as determined by TTE will be assessed using summary statistics. Observations and change from Baseline will be summarized by treatment at each timepoint and the maximum change from Baseline will be determined for each patient.

11.3.7.2 Adverse Events

AEs will be mapped to system organ classes and preferred terms using the Medical Dictionary for Regulatory Activities (MedDRA). AEs will be monitored during the study and the data analyzed with respect to overall incidence as well as severity and potential relationship of AEs to study medication, AEs with onset on or after the first dose of study medication, or with an onset before the first dose of study medication that increase in severity on or after the first dose of study medication, will also be monitored. Treatment-emergent AEs will be summarized for the Safety Analysis population by MedDRA system organ class and preferred term, and by severity and relationship to treatment. Severe and life-threatening AEs, SAEs, AEs leading to study withdrawal, if any, will be presented in data listings.

11.3.7.3 12-lead Electrocardiogram

The RR, PR, QRS, and QT intervals will be measured. HR will be calculated as $60/(RR \text{ times } 1000)$ (with RR expressed in ms) and rounded to the nearest integer.

QTc will be calculated using the manually over-read QT values per the standard procedures of the central ECG laboratory. Each individual ECG QT value will be corrected for HR. The measured QT data will be corrected for HR using the Fridericia method (QTcF) as per the following formulae/method (with QT, RR and QTc expressed in ms):

$$QTcF = \frac{QT}{\frac{RR^{0.33}}{1000}}$$

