4.2 Stopping Criteria

For Part 1, as each patient will receive several, ascending single doses, there are stopping criteria for which further dosing of an individual patient must be suspended, and also stopping criteria for the study to be considered by SRC.

For Part 2, as each patient will receive 9 days of study drug treatment (including 2 days of single-blind placebo and 7 days of DB active or placebo), there are dose-modification criteria and stopping criteria for individual patients, as well as stopping criteria for the study to be considered by SRC.

4.2.1 *Stopping Criteria for an Individual Participant in Part 1 (SAD)*

If the following events occur, as determined by investigator assessment, dosing of a patient must be suspended, AE/SAE forms completed as applicable, and the event reviewed by the SRC. The SRC may decide to perform selected unblinding pertaining to one or several periods for a given patient or recommend that further dosing of the patient be suspended. The following is a list of possible criteria for suspension of dosing of an individual and review of the data by the SRC:

- A patient has drug-related cardiac ischemia, as determined by investigator (Note: The whole context [ie, clinical symptoms, ECG, and cardiac biomarkers such as troponin, CK-MB, cardiac imaging, and coronary angiograms, if applicable] should be taken into account by the investigator in making that determination since patients enrolled in the study are likely to have an abnormal ECG and/or elevated and/or fluctuating troponin at Baseline in relation to their heart failure condition. This information will also be submitted for subsequent central adjudication).
- A patient has an increase in the maximal SET > 75 ms on 2 sequential TTE recordings based on site evaluations.
- A patient has clinically significant and drug-related changes in his/her vital signs that are persistent over a period of time such as a new arrhythmia, systolic BP < 90 or > 170 mm Hg, or HR < 40 or > 100 bpm. The diagnosis and clinical significance of a new arrhythmia will be adjudicated by the SRC as it relates to this stopping criterion, including core lab assessments as appropriate.
- A patient experiences a drug-related SAE (including, but not limited to, serious unexpected suspected adverse reactions [SUSARs] or coronary ischemic events).
- A patient has a QTc interval > 500 ms (Fridericia's correction, average of triplicate ECGs) not attributable to pacing or prolonged QRS duration.

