5.1 Inclusion Criteria

This study is to be performed in patients with HFrEF due to any etiology. Each patient must meet the following criteria to be included in this study:

1. Able to understand and comply with the study procedures, understand the risks involved in the study, and provide written informed consent according to federal, local, and institutional guidelines before the first study-specific procedure
2. Men or women 18 to 80 years of age at the Screening visit
3. Body mass index (BMI) 18 to 40 kg/m², inclusive, at the Screening visit and all required assessments can be reliably performed.
4. Sinus rhythm or stable atrial pacing with mean resting HR 50-95 beats per minute (bpm), inclusive (Patient will be ineligible to dose if, on Day 1, the predose HR measurement is ≥ 95 bpm. Heart rate is the mean of 3 measurements taken 1 minute apart. A single measurement would not make a patient ineligible.)
5. Has stable, chronic HFrEF of moderate severity as defined by all of the following:

- For the first 3 patients in each MAD Cohort testing a new (higher) daily dose: documented LVEF 25% to 35% during Screening (as confirmed by ECHO Central Lab)
- For other patients in the MAD Cohorts (and all patients in SAD Cohorts): documented LVEF 15% to 35% during Screening (as confirmed by ECHO Central Lab)
 - LVEF must be confirmed with second screening ECHO to be performed at least 7 days after initial screening ECHO. Results of both must meet inclusion criteria and must be received from core lab prior to dosing. In the event of extended screening windows due to SRC reviews, effort should be made to ensure second ECHO is near planned time of randomization.
- Chronic medication for the treatment of heart failure consistent with current guidelines that has been given at stable doses for \geq 2 weeks with no plan to modify during the study. This includes treatment with at least one of the following unless not tolerated or contraindicated: beta-blocker, angiotensin converting enzyme (ACE) inhibitor/angiotensin receptor blocker (ARB)/angiotensin receptor neprilysin inhibitor (ARNI).

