11.3 Statistical Analysis

Before database lock, a statistical analysis plan (SAP) for clinical data and an analysis plan for PK will be prepared that will contain full details of all planned analyses. The analyses presented here represent an outline of the intended methodology.

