11.3.7.3.1 ECG Numeric Variables

HR, PR, QRS, and QTcF will be summarized using descriptive statistics. The change from Baseline of these ECG parameters at each timepoint will be listed for each patient. For each timepoint of measurement, the changes from Baseline will be summarized. The relationship between HR/ECG intervals and time will be plotted.

Separate analyses will be performed in patients who are not paced and have no prolonged QRS at Baseline.

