11.3.7.3.2 Categorical Analysis

The incidence count and percentage of patients with any postdose QTcF values of > 450 ms, > 480 ms, and > 500 ms will be tabulated for all patients. Patients with QTc values > 500 ms will be listed with corresponding Baseline values, $\Delta QTcF$, and Baseline and treatment HR. The incidence count and percentage of patients with $\Delta QTcF$ increase of > 30 ms and > 60 ms will be tabulated.

A separate QTcF analysis will be performed in patients who are not paced and have no prolonged QRS at Baseline.

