AD, admission; AE, adverse event; BP, blood pressure; CK-MB, creatine kinase-MB; eCRF, electronic case report form; D/C, discharge; ECG, electrocardiogram; HR, heart rate; ICF, informed consent form; IMP, investigational medicinal product; PK, pharmacokinetic; SAE, serious adverse event; SRC, Safety Review Committee; TTE, transthoracic echocardiography.

- ^a All predose assessments should be performed within 2 hours of administering the oral dose of MYK-491 or placebo, with the following exceptions: predose or trough PK blood samples should be taken within 1 hour predose, and ECG telemetry monitoring should be initiated at least 1 hour prior to dosing.
- ^b The patient will be discharged from clinical research unit on Day 3 after all procedures have been completed and the investigator deems it safe.
- ^c Update medical history at Day -1, if needed.
- ^d At Screening and Day -1, a complete physical examination will be conducted including a neurological examination (gross motor and deep tendon reflexes), height and weight, and assessment of the following: general appearance, skin, head and neck, mouth, lymph nodes, thyroid, abdomen, musculoskeletal, cardiovascular, neurological, and respiratory systems. At 6 hours postdose and at the Follow-up visit, an abbreviated physical examination (pulmonary, cardiac, abdominal, and other systems related to any symptoms) will be conducted.
- ^e Vital signs will be taken at Screening, at Day -1, predose, and at 3, 6, 12, and 24 hours postdose, and at the Follow-up visit. Vital signs include temperature, HR, and BP after resting for at least 5 minutes. HR and BP taken predose, 6 hours, and 24 hours postdose will be obtained with the patient in the supine position, 1 time after standing for 2 minutes and 1 time after standing for 5 minutes. All other HR and BP measurements should be the mean of 3 measurements taken in supine position, and BP should be taken via an automated recorder. On Day 1, patient will be ineligible to dose if HR \geq 95 bpm at predose.

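### Section 11.3.7.3 derives ECG heart rate as 60/(RR times 1000) with RR in ms, which rounds to 0 bpm for any physiological RR; the conversion should be 60000/RR (minor correction)

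*Combined protocol and SAP*

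**What the plan says.** Section 11.3.7.3 lists RR among the intervals measured on the 12-lead ECG and then defines heart rate from it: "HR will be calculated as $60/(RR \text{ times } 1000)$ (with RR expressed in ms) and rounded to the nearest integer". The next paragraph, on the Fridericia correction, again puts RR in ms, so the unit is stated twice. I found no other derivation of heart rate in the documents.

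The derived value feeds these outputs:

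- Section 11.3.7.3.1: "HR, PR, QRS, and QTcF will be summarized using descriptive statistics". The same section calls for changes from Baseline at each timepoint, listed by patient and summarized.
- Section 11.3.7.3.1, on the plot: "The relationship between HR/ECG intervals and time will be plotted".
- Section 11.3.7.3.2: the listing of patients with QTc above 500 ms is to show "Baseline and treatment HR".

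Other uses of heart rate are not tied to this rule:

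- Appendix 1, Table 3, footnote e treats it as a vital sign: "Vital signs include temperature, HR, and BP after resting for at least 5 minutes".
- Section 5.1, on eligibility: "Heart rate is the mean of 3 measurements taken 1 minute apart".
- Section 4.2.1 places the stopping limits under vital signs: "systolic BP < 90 or > 170 mm Hg, or HR < 40 or > 100 bpm".

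Section 11.3 describes its own status: "The analyses presented here represent an outline of the intended methodology". A SAP is to follow before database lock.

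**The concern.** Converting an RR interval to a rate needs RR in seconds, so a value in ms must be divided by 1000 before it divides 60. The written rule multiplies by 1000 instead. The likely cause is a misplaced bracket, since (60/RR) times 1000 would be correct.

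What is at stake is one derived variable in the ECG safety outputs. A programmer who follows the rule produces zeros. One who quietly uses the usual conversion produces sensible numbers that do not match the written derivation. In the QTc listing, heart rate is the context for reading a rate-corrected interval, so a zero there removes the information the listing is meant to give.

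**Working it through.** **Inputs**

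- Rule: 60/(RR × 1000), rounded to an integer (Section 11.3.7.3).
- Unit of RR: ms (Section 11.3.7.3, stated twice).
- Scale of heart rate elsewhere: 50 to 95 bpm for eligibility (Section 5.1); below 40 or above 100 bpm as stopping limits (Section 4.2.1).
- Assumed range for the check: 30 to 200 bpm, deliberately wider than the eligibility range.

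The plan gives no worked heart-rate value, so there is no figure of its own to reproduce.

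**Step 1: the rule as written against the unit conversion**

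For each true rate, RR = 60000/HR.

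| True HR (bpm) | RR (ms) | Written: 60/(RR × 1000) | After rounding | 60000/RR |
|---|---|---|---|---|
| 30 | 2000 | 0.00003 | 0 | 30 |
| 50 | 1200 | 0.00005 | 0 | 50 |
| 75 | 800 | 0.000075 | 0 | 75 |
| 95 | 631.6 | 0.000095 | 0 | 95 |
| 200 | 300 | 0.0002 | 0 | 200 |

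**Step 2: size of the error**

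Correct divided by written = (60000/RR) / (60/(1000 × RR)) = 60000 × 1000/60 = 1,000,000, whatever the RR.

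**Step 3: when would the written rule give anything but 0?**

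Setting 60/(RR × 1000) = 0.5 gives RR = 60/500 = 0.12 ms, far below any physiological interval.

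**Step 4: other readings**

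- RR in seconds in the same formula: at RR 2 s, 60/2000 = 0.03; at RR 0.3 s, 60/300 = 0.2. Both still round to 0, and this reading contradicts the stated unit.
- (60/RR) × 1000 with RR in ms: returns 30, 50, 75, 95 and 200 bpm for the five rows above.
- 60/(RR/1000) with RR in ms: the same five values.

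Moving the 1000 out of its place as a multiplier in the denominator recovers the bpm scale used in Sections 5.1 and 4.2.1. Changing the unit of RR to seconds does not.

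**Step 5: effect on a change from Baseline (assumed example)**

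A rise from 65 to 80 bpm is RR 923.1 to 750 ms. The written rule gives 0.000065 and 0.00008, which both round to 0, so the reported change is 0 − 0 = 0. The correct change is +15 bpm.

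**The case against.** The strongest objection is provenance. The error consists only of where a bracket falls, and the text was read from PDF by a program. The QTcF formula just below also has its 1000 grouped oddly as extracted, so one faulty reading could explain both. This stands in part and is why the source page must be checked first. It is weaker for heart rate than for QTcF: the heart-rate rule is an inline phrase with the operator spelled out as a word, while the QTcF formula is a stacked fraction whose layout can collapse on extraction. No QTcF error is claimed here.

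The second objection is that little follows from it. This also largely stands. Section 11.3 is an outline ahead of a SAP, the study does no formal hypothesis testing, and no decision rule is shown to use this heart rate. The intended meaning is clear from the units, and a column of zeros would be caught at once. These points limit the severity. They do not make the written rule right, and the time before the SAP is the natural point to correct it.

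A smaller point also stands: Section 11.3.7.3.2 does not say that the heart rate in its listing is the derived one. That is a reasonable inference from where the listing sits, under the 12-lead ECG heading.

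**Conclusion.** The rule is wrong as written. It understates heart rate by a factor of 1,000,000 and, after the stated rounding, returns 0 bpm for every physiological RR. The arithmetic is certain. That the sponsor's page carries the same bracket is likely but rests on the extracted text.

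The outputs affected are the ECG heart-rate summary, its changes from Baseline and its time plot (Section 11.3.7.3.1), and very likely the heart rates in one listing (Section 11.3.7.3.2). QTcF uses RR directly. The vital-sign, eligibility and stopping heart rates are not shown to depend on the rule. Severity is minor.

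**What to change.** Confirm the line in Section 11.3.7.3 against the source page. If it reads as quoted, replace it with: HR (bpm) = 60/(RR/1000) = 60000/RR, with RR in ms, rounded to the nearest integer. Do this before the rule is copied into the SAP or the programming specifications.

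The cost is a look at one page and a one-line text correction. Section 13.4 already lets the sponsor correct typographical errors by Administrative Letter. Data collection and patients are not affected.

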If the following events occur, as determined by investigator assessment, dosing of a patient should be modified by skipping one dose of study drug and resuming dosing at a lower dose (25% to 50% lower). The lower dose to be administered for a given cohort will be determined by SRC and communicated along with starting dose. [REDACTED]

- An increase in the maximal SET > 75 ms on 2 sequential TTE recordings based on site evaluations
- A patient has 2 successive echocardiograms that show a > 50% relative increase from Baseline in at least 2 contractility indices (LVSV [derived from LVOT-VTI], LVEF, or LVFS).

Note: Day 3, predose echo in the morning should be used as Baseline for local site evaluation.

In addition, in case of an AE, DB treatment may be temporarily suspended, as determined by the investigator. In such cases, the Sponsor medical monitor should be contacted without delay.

4.2.4 *Stopping Criteria for an Individual Participant in Part 2 (MAD)*

If the following events occur, as determined by investigator assessment, dosing of a patient must be terminated, AE/SAE forms completed as applicable, and Sponsor should be informed without delay:

- Drug-related coronary ischemia, as determined by investigator
Note: Whole context ie, clinical symptoms, ECG, cardiac biomarkers such as troponin, CK-MB, cardiac imaging, and coronary angiograms, if applicable, should be taken into account by the investigator in making that determination since patients enrolled in the study are likely to have elevated and/or fluctuating troponin and/or abnormal ECGs at Baseline in relation to their heart failure condition. This information will also be submitted for subsequent central adjudication.
- The patient has clinically significant and drug-related changes in his/her vital signs that are persistent over a period of time such as a new arrhythmia, systolic BP < 90 or > 170 mm Hg, or HR < 40 or > 100 bpm. The diagnosis and clinical significance of a new arrhythmia will be adjudicated by the SRC as it relates to this stopping criterion.
- A patient experiences a drug-related SAE (including, but not limited to, SUSARs or coronary ischemic events).
- A patient has a QTcF interval > 500 ms (Fridericia's correction, average of triplicate ECGs) not attributable to pacing or prolonged QRS duration.
- Any patient fulfills the criteria for potential drug-induced liver injury (Hy's Law). These include:

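### As it reads in Section 11.3.7.3, the QTcF formula puts the 1000 outside the power, so with RR in ms it returns values about 102 times too large; the heart-rate formula beside it misplaces the 1000 as well (check the exponent's position on the source page).

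*Combined protocol and SAP*

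**What the plan says.** Section 11.3.7.3 (12-lead Electrocardiogram) makes four statements that matter here.

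- Method: "The measured QT data will be corrected for HR using the Fridericia method (QTcF").
- Units: the formula is introduced "as per the following formulae/method (with QT, RR and QTc expressed in ms").
- Formula: in the typesetting code of the machine-read text it begins "QTcF = \frac{QT}{\frac{RR^{0.33}}{1000", followed only by closing braces. That is QT / (RR^0.33 / 1000).
- Who computes it: "QTc will be calculated using the manually over-read QT values per the standard procedures of the central ECG laboratory".

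The same section defines heart rate, in running text, as 60 divided by the product of RR and 1000, with RR in ms and the result rounded to a whole number.

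QTcF is used further on. Section 11.2.1 lists ECG intervals among the primary safety measures. Section 11.3.7.3.1 summarizes QTcF and its change from Baseline. Section 11.3.7.3.2 counts patients with "any postdose QTcF values of > 450 ms, > 480 ms, and > 500 ms", and patients with an "increase of > 30 ms and > 60 ms will be tabulated". Section 11.3.7.3.4 allows, but does not require, a concentration-QTc regression.

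**The concern.** Fridericia's correction divides QT by the cube root of RR expressed in seconds. With RR in ms, the division by 1000 has to happen inside the power. Here it happens after the power has been taken, and the two operations do not commute. The stated units, the stated method and the formula therefore cannot all be right.

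This is the only explicit QTcF definition in the text available. If it were carried literally into a specification, the absolute QTcF categories would carry no information because every patient would fall in all of them. The change categories would respond to sub-millisecond differences. These tables belong to a primary safety measure, so the definition should be usable as written.

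**Working it through.** The plan states no numerical QTcF result, so there is no figure to reproduce. The check evaluates the formula as it reads against the one its units and method require.

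**Inputs**
- Formula, units and method: Section 11.3.7.3.
- Heart-rate range at entry: 50 to 95 bpm (Section 5.1, criterion 4), so RR = 60,000/HR runs from 1200 ms to about 632 ms.
- QT = 400 ms: an assumption for illustration, since the documents give no QT data. The ratio in step 1 does not depend on it.

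**Step 1: ratio**

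As it reads: A = QT / (RR^0.33 / 1000) = 1000 × QT / RR^0.33.

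Required: B = QT / (RR/1000)^0.33 = 1000^0.33 × QT / RR^0.33.

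A / B = 1000 / 1000^0.33 = 1000^0.67 = 102.33 for every QT and RR. If B uses the exponent 1/3, the ratio is 102.16 to 102.47 over 40 to 100 bpm, so the choice of exponent is immaterial.

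**Step 2: examples with QT = 400 ms**

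| HR (bpm) | RR (ms) | A, as it reads (ms) | B, corrected, exponent 0.33 (ms) |
|---|---|---|---|
| 50 | 1200 | 38,542 | 376.6 |
| 60 | 1000 | 40,932 | 400.0 |
| 75 | 800 | 44,060 | 430.6 |
| 95 | 632 | 47,634 | 465.5 |

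The 60 bpm row is a check on its own: at RR = 1 s a rate correction must return the measured QT.

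**Step 3: absolute categories**

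A exceeds 500 ms once QT > 500 × RR^0.33 / 1000. That is 5.59 ms at 40 bpm and 4.13 ms at 100 bpm. No real ECG has a QT that short, so every ECG would pass the 450, 480 and 500 ms limits.

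**Step 4: change categories**

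Differences scale by the same factor (taking B with exponent 0.33 as the true value). A rise is counted as more than 30 ms once the true rise exceeds 30 / 102.33 = 0.29 ms, and as more than 60 ms once it exceeds 60 / 102.33 = 0.59 ms. Patients with no rise, or only falls, are not counted, so these percentages need not reach 100%.

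**Step 5: heart rate**

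At RR = 1000 ms the stated formula gives 60 / (1000 × 1000) = 0.00006, which rounds to 0 bpm. The form 60 / (RR/1000) gives 60 bpm.

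**Step 6: could seconds have been meant?**

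With QT = 0.400 s and RR = 1.0 s, the QTcF formula returns 0.400 / (1/1000) = 400, the right value in ms. But the section states ms for QT and RR. The heart-rate formula is not rescued either: 60 / (1.0 × 1000) = 0.06, again 0 bpm after rounding.

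**The case against.** The strongest objection is that the error may not be in the plan. The evidence is a stacked equation rebuilt by a program, and everything turns on whether the superscript belonged to RR or to the fraction RR/1000. A lost pair of parentheses would produce this result. That stands as a reason to check the source page before acting. It is weakened by the heart-rate formula, which sits on a running line and puts the multiplication by 1000 in words; a displaced superscript cannot explain that. It makes a source error plausible without proving where the exponent stood in the display.

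Second, the section names the method and hands the calculation to the central ECG laboratory's procedures, and a QTcF near 40,000 ms would be noticed at once. This stands, and it limits the point to a definition that needs correcting.

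Third, Section 11.3 calls its content an outline and leaves full detail to an SAP written before database lock. This also stands: the available text contains no SAP formula, so nothing shows that the error is repeated there.

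A reader might go further and infer that QTcF-based eligibility or stopping decisions would be wrong. The documents do not support that. Those rules, such as the Part 2 individual criterion in Section 4.2.4, "A patient has a QTcF interval > 500 ms (Fridericia's correction, average of triplicate ECGs"), name the correction and do not refer to the formula in Section 11.3.7.3.

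**Conclusion.** Wrong as written, subject to confirming the exponent's position on the source page. With QT and RR in ms, the QTcF formula is not Fridericia's correction and overstates every value by a factor of 1000^0.67, about 102. The heart-rate formula in the same section is also wrong and returns 0 bpm for any plausible RR.

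The consequence is conditional on literal programming. In that case the three absolute QTcF categories would each read 100%, while the two change categories would be heavily inflated. Two stronger readings go too far: that the change categories would also read 100%, which fails because they count only increases, and that reported QTcF values would be wrong, which the laboratory's procedures would probably prevent. The factor rests on the stated units and does not depend on the assumed QT. The point is worth correcting before any programming because it concerns the definition of a primary safety measure and costs almost nothing to put right.

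**What to change.** 1. Compare the displayed equation with the source page.
2. If the exponent is on RR alone, replace the formula with QTcF = QT / (RR/1000)^0.33, or with exponent 1/3, with QT, RR and QTcF in ms.
3. Replace the heart-rate formula with HR = 60 / (RR/1000), RR in ms. This is needed whatever step 1 shows.
4. Make sure that any SAP, programming specification or data-transfer agreement with the central ECG laboratory uses the corrected forms. A test record with QT 400 ms and RR 1000 ms should return 400 ms and 60 bpm.

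The cost is one line per formula. Section 13.4 allows an Administrative Letter for correcting obvious errors and inconsistencies, with ethics committee notification or approval where local rules ask for it. No design, data collection or sample-size change follows.
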